6.3 Statistical analysis

A single principal analysis is anticipated at 12 months after the last woman is recruited. The Data Monitoring Committee will determine the frequency of confidential interim analyses, but at present these are planned on four occasions during the data collection period.

All analyses within the RCT will be based on the intention-to-treat principle. All outcomes in both trials will be described with the appropriate descriptive statistics where relevant: mean and standard deviation for continuous and count outcomes, or medians and inter-quartile range if required for skewed data, numbers and

percentages for dichotomous and categorical outcomes (for example subjective recurrence of prolapse).

Analysis of the primary outcome (POP-SS) will estimate the mean differences (and 95% confidence interval) between the intervention and control groups using a general linear model that adjusts for the minimisation covariates and other important prognostic covariates, including the baseline symptom score, at 12 months after surgery. A similar analysis will be used to analyse the primary outcome at 6 and 24 months.

All secondary analyses will be analysed in a similar manner but using the appropriate generalised linear model (for example logistic regression for dichotomous data such as subjective prolapse failure, Poisson or negative binomial regression for count data such as number of nights in hospital) or time to event methods (e.g. Cox regression on time to further surgery) where required. We will explore analysing outcomes at all time points simultaneously using for example, Generalised Estimating Equations or Generalised Linear Latent and Mixed Models, and relevant link functions, to explore changes in outcome over time.

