The questionnaire at each time-point will be identical and collect the same patient-reported outcome measures used in PROSPECT: prolapse symptoms; urinary, bowel and sexual function; EQ-5D; treatment failure including the need for additional surgery, pessaries, drugs or physiotherapy; postoperative complications including the need for additional surgical or conservative treatment; costs; and cost-effectiveness. In addition to postal questionnaire, HES (England) and ISD (Scotland) data will be requested to verify all preceding hospital re-admissions. Furthermore, case report verification will be carried out in the three lead centres (Aberdeen, Manchester and Plymouth) after the 6 year data collection is complete to verify and validate the other two data collection methods.

During the extended follow-up phase the same efficient retention system used in PROSPECT will be employed to ensure questionnaire return rates are maximised. This involves sending a reminder letter and further questionnaire three weeks after the original questionnaire is issued and not returned, followed by a postal or phone call reminder for continuing non-responders. The death notification service provided by the Health and Social Care Information Centre (HSCIC) will be utilised to minimise the risk of issuing a questionnaire to a participant who has subsequently died.

Loyalty and interest in the long term follow-up study will be maintained by continuing to send annual newsletters and Christmas cards to trial participants.

Primary outcome and power calculation

The primary clinical outcome measure for the main PROSPECT trial is the prolapse symptom score (POP-SS) at 12 months. In the long term follow-up study, the primary clinical outcome measure will be the POP-SS at 14 years. We estimate that if 400 patients in each arm of the primary trial respond to a questionnaire at 14 years (i.e. the current response rate is maintained over time), this will provide 96% power to detect a mean difference of 2 points (assuming SD=7 and alpha=0.025). If the response rate were to fall to 50% by 14 years, we would have 78% power to detect a difference of 2 POP-SS points.

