## Primary Outcomes

The primary patient-reported outcomes are symptoms of prolapse, measured as:

- the number and frequency of prolapse symptoms on the Pelvic Organ Prolapse Symptom Scale (POP-SS) at one year after surgery
- a quality of life outcome measured as the overall effect of prolapse symptoms on everyday life.

The POP-SS is a composite outcome measure comprising seven patient recorded items each relating to a different symptom. Each item has an ordinal response schedule with five levels of response based on frequency of the symptom (“never”, “occasionally”, “sometimes”, “most of the time” and “all of the time”) and is scored from 0 to 4 respectively. The overall POP-SS score is the sum of each item score and can range from zero to 28.

For the primary analysis, individual items that are missing will be assumed to have a value of zero. However, this assumption will be tested in sensitivity analyses. If all seven questions are unanswered, then the POP-SS score will be treated as missing.

The primary economic outcome measure of cost effectiveness is incremental cost per QALY (QALYs based on the EQ-5D). The cost effectiveness analysis is set out separately in the economic analysis plan.

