## **Statistical Methods**

### **General Methods**

The statistical analysis of the RCTs will be based on all women as randomised, irrespective of subsequent compliance with the treatment allocated (intention to treat). The principal comparisons will be:

- In women having a primary prolapse repair,
  - a standard anterior and/or posterior repair will be compared with a standard repair using a biological graft inlay; and
  - a standard anterior and/or posterior repair will be compared with a standard repair using a non-absorbable or combined mesh inlay.
- In women having a secondary prolapse repair,
  - a standard anterior and/or posterior repair will be compared with a standard repair using a non-absorbable or combined mesh inlay; and
  - a standard anterior and/or posterior repair will be compared with a mesh kit procedure using an introducer device.

The two trials are being considered independently because different surgical options are considered to be appropriate for clinical reasons. Women who are not randomised but who are in the Comprehensive Cohort group will be analysed according to the operation actually carried out.

Descriptive statistics will be tabulated by treatment allocation for all outcomes (mean and SD for continuous data, proportions for binary data). Treatment effects will be estimated with 95% confidence intervals for all outcomes (mean differences for continuous data, odds ratios for binary data). Statistical significance will be at the 5% level and corresponding confidence intervals will be derived. Analyses will be conducted using SAS v9.3.

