## Sample Size and Power Calculation

In an average population of women having prolapse surgery, about 70% will be having a primary procedure. Two comparisons will be made:

- a standard repair versus a standard repair using a biological graft inlay; and
- a standard repair versus a standard repair using a non-absorbable or combined mesh inlay.

Pilot data have shown that a conservative estimate of the standard deviation of the primary patient-reported outcome POP-SS is 8 units. A difference in means of 2 units would represent an improvement in the response to a POP-SS question, for example, a feeling of something coming down or in the vagina, from 'Most of the Time' to 'Occasionally'. To detect a standardised difference of 0.25 with 90% power and alpha equal to 0.025 (to maintain the nominal p value at 0.05 with two tests being used), we would need to randomise 400 women to each arm of the study. Best efforts using evidence based techniques will be employed to maximise the response rate at follow up. Nevertheless, we feel it prudent to inflate the estimated sample size for 15% dropout at one year requiring approximately 1450 women having primary surgery to be recruited to the trial. Adjusting for baseline covariates and minimising the loss to follow up will potentially improve this power. A trial of this size would also be adequately powered to detect important differences in the economic and secondary outcomes.

It is estimated that the other 30% of women requiring anterior and/or posterior repair will receive a secondary or subsequent repair. Therefore, during the proposed time period required for recruiting 1450 women to the primary repair RCT above, it is anticipated approximately 620 women having secondary surgery will be eligible and will be willing to be randomised. Within the secondary RCT two comparisons will be made:

- a standard repair versus a standard repair using a non-absorbable or combined mesh inlay; and

- a standard repair versus a mesh kit procedure.

It would be possible to detect with 90% power and alpha equal to 0.025 a standardised effect size of 0.38 which equates to 3 points on the POP-SS scale (this estimated effect detectable has been calculated adjusting for potential 15% dropout at one year). The pilot data from IMPRESS indicated that women having secondary repairs have a higher level of symptoms at baseline. Therefore it is biologically plausible that these women may show a larger benefit from the options available.

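### The 0.025 per-comparison alpha used to size the trials is not carried into the analysis rules, so the chance of a false positive on POP-SS at 12 months is about 9% per trial, not the stated 5%

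*SAP*

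**What the plan says.** **Design.** The SAP's sample-size section, repeated in protocol section 2.7.2, sizes the primary trial for a 2-point POP-SS difference (SD 8, 90% power) with "alpha equal to 0.025 (to maintain the nominal p value at 0.05 with two tests being used". For the secondary trial it says: "It would be possible to detect with 90% power and alpha equal to 0.025 a standardised effect size of 0.38". Protocol Appendix IV uses 0.025 again for the long-term follow-up.

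**Analysis.** SAP General Methods says "Treatment effects will be estimated with 95% confidence intervals for all outcomes" and then "Statistical significance will be at the 5% level and corresponding confidence intervals will be derived". Protocol section 6.3 agrees on the interval: "Analysis of the primary outcome (POP-SS) will estimate the mean differences (and 95% confidence interval) between the intervention and control groups". Neither document names Bonferroni, Holm, Dunnett, a testing order or any other procedure for the pair of comparisons. The only stricter level in either analysis section is the 0.01 threshold for exploratory subgroup interactions.

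**Which estimate.** The SAP section on primary and secondary outcomes analyses the three-arm stratum RCT1 on its own. It then combines RCT1 with RCT1B, and RCT1 with RCT1C, to give a further estimate of each effect. It does not say which estimate decides. The secondary trial is handled in the same way, except that RCT2 is not pooled with RCT2D.

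**The concern.** The design makes a specific promise about the error rate over two tests, and the larger sample was justified by it. The analysis rules do not keep that promise. For a primary-outcome p-value between 0.025 and 0.05, General Methods would report a difference from standard repair, while the level on which the trial was sized would not. The main conclusion about either mesh could then depend on which part of the SAP is cited after the results are known, although protocol section 2.6 undertakes to predefine all analyses.

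**Working it through.** **1. Was 0.025 really used in the design?** Per-arm size for two means is n = 2(z₁₋α/₂ + z₀.₉₀)² / d², with d = 2/8 = 0.25.

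- Two-sided 0.025: 2 × (2.241 + 1.282)² / 0.0625 = 397, rounded up to 398 (stated: 400).
- Two-sided 0.05: 2 × (1.960 + 1.282)² / 0.0625 = 336, rounded up to 337.

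One-sided 0.025 also gives 337 and one-sided 0.05 gives 275, so only two-sided 0.025 reproduces the stated figure. For the secondary trial, 620 × 0.85 / 3 = 175.7 per arm gives a detectable effect of (2.241 + 1.282) × √(2/175.7) = 0.376 (stated: 0.38). The split was part of the design.

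**2. Correlation between the two contrasts.** Both use standard repair, so they are positively correlated. Inputs are the counts in SAP Tables 2 and 3. Within a stratum the weight is w = 1/(1/n_A + 1/n_X). The variance of a combined contrast, in units of SD², is 1/Σw. The covariance is the product of the shared stratum's two weight fractions divided by its number of controls.

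- *Primary, combined strata.* A–B weights 127.2 and 89.7 give variance 0.00461. A–C weights 127.0 and 57.5 give variance 0.00542. Covariance = (127.2/217.0)(127.0/184.5)/253 = 0.00160. Correlation = 0.00160/√(0.00461 × 0.00542) = 0.32.
- *Primary, RCT1 alone.* (1/253)/√(0.00786 × 0.00787) = 0.50.
- *Secondary, RCT2 + RCT2B for synthetic and RCT2 for kit.* Variances 0.0374 and 0.0644; covariance (12.0/26.7)/24 = 0.0187; correlation 0.38.
- *Secondary, RCT2 alone.* (1/24)/√(0.0833 × 0.0644) = 0.57.

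**3. Chance of at least one false positive.** This is 1 − P(|Z₁| < c, |Z₂| < c) for a bivariate normal pair, with c = 1.960 at 0.05 and c = 2.241 at 0.025.

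| Analysis | Correlation | Each at 0.05 | Each at 0.025 |
|---|---|---|---|
| Primary, combined | 0.32 | 9.5% | 4.8% |
| Primary, RCT1 alone | 0.50 | 9.1% | 4.6% |
| Secondary, combined for synthetic | 0.38 | 9.4% | 4.8% |
| Secondary, RCT2 alone | 0.57 | 8.9% | 4.5% |

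Independent tests would give 9.75% and 4.94%.

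**4. Power at the numbers actually randomised.** Assume SD 8 and 15% loss. SE = 8 × √(variance/0.85), and power = Φ(difference/SE − c).

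| Comparison with standard repair | Difference | SE | At 0.05 | At 0.025 |
|---|---|---|---|---|
| Primary, synthetic (combined) | 2 | 0.589 | 92% | 88% |
| Primary, biological (combined) | 2 | 0.639 | 88% | 81% |
| Secondary, synthetic (combined) | 3 | 1.68 | 43% | 32% |
| Secondary, mesh kit (RCT2) | 3 | 2.20 | 28% | 19% |

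The choice of deciding estimate matters more than the choice of level. For synthetic mesh in RCT1 alone, SE = 8 × √(0.00786/0.85) = 0.769, and power at 0.025 is Φ(2/0.769 − 2.241) = 64%.

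**The case against.** **The 5% could be an overall level.** The General Methods sentence is generic and never says that 5% applies per comparison. Read with the sample-size section, it could mean 5% overall with 0.025 per test. That reading is possible, but 95% intervals for all outcomes correspond to 5% per comparison, and no method is given for reaching 5% overall. What stands is that the sample-size paragraph is a power calculation, not a decision rule. A reader might infer that the design formally declares p between 0.025 and 0.05 non-significant. It does not; it only sizes the trial on 0.025.

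**Distinct treatments need no adjustment.** This is a respectable position, but these documents chose the opposite and gave their reason. They may change course only by withdrawing the claim.

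**A second primary outcome.** Both documents list, under primary outcomes, "a quality of life outcome measured as the overall effect of prolapse symptoms on everyday life". A reader might infer four confirmatory tests per trial and an error rate as high as about 18%, since 1 − (1 − 0.094)² = 0.18. The documents do not support that. Protocol section 6.3 and the SAP's sensitivity, outcome-analysis and sample-size sections all treat POP-SS as the single primary outcome, and Appendix IV states: "The primary clinical outcome measure for the main PROSPECT trial is the prolapse symptom score (POP-SS) at 12 months". The 18% also assumes that symptom frequency is independent of the effect of those same symptoms on daily life, which is implausible. Assumed correlations of 0.9 to 0.5 would give about 13% to 17%, but the documents provide no value. The everyday-life item is a labelling inconsistency, and restoring the split does not require demoting it.

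**Power.** A reader might infer that using 0.025 costs nothing because the sample size assumed it. That is true only against the targets of 1450 and 620. The SAP tables sum to 1353 and 155.

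**Conclusion.** The point holds for the two comparisons on POP-SS at 12 months. The analysis rules, as written, give about 9% per trial (9.1% to 9.5% primary, 8.9% to 9.4% secondary) against a stated 5%. The figures rest on two-sided tests, normal test statistics, equal variances across arms, the randomised counts in SAP Tables 2 and 3, and reading the 5% level as applying to each comparison. They do not depend on the SD or on the everyday-life item. Only a result with p between 0.025 and 0.05 would change its label, but that label is the trial's main conclusion, so the rule must be settled before results are seen.

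**What to change.** In SAP General Methods:

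1. State that, within each trial, the two principal comparisons on POP-SS at 12 months are judged at two-sided 0.025 with 97.5% intervals, or by Holm at 5% overall. Either gives 4.5% to 4.8% when neither mesh differs from standard repair. Standard Dunnett does not fit directly, because the combined models are fitted separately with only partly shared controls.
2. Name the deciding estimate for each comparison: the three-arm stratum alone or the combined strata. Because POP-SS at 12 months will also be analysed with a composite binary/linear model, say which estimate from which model is judged.
3. Label all other 5% and 95% results, including the everyday-life item, as unadjusted.
4. Bring the interval in protocol section 6.3 into line.

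If the sponsor prefers no adjustment, remove the statement that 0.05 is maintained over two tests from SAP Sample Size and protocol section 2.7.2, and report the comparisons openly as unadjusted.

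The cost is a few sentences, primary intervals about 14% wider (2.241/1.960 = 1.14), and the power losses shown in the second table of the working. Those losses are modest in the primary trial. In the secondary trial power is already low at either level.

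### The two principal comparisons in each trial were sized at 2.5% each but are to be judged at 5% each, so the overall 5% error that the plan says it maintains is not delivered

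*SAP*

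**What the plan says.** In the SAP's Sample Size and Power Calculation, the primary trial is sized "with 90% power and alpha equal to 0.025 (to maintain the nominal p value at 0.05 with two tests being used"). Protocol 2.7.2 gives the same level and reason. From "a conservative estimate of the standard deviation of the primary patient-reported outcome POP-SS is 8 units" and a target difference of 2 units, the conclusion is that "we would need to randomise 400 women to each arm of the study". The secondary trial is sized at the same 0.025, but there no reason is given.

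The SAP's General Methods section, which holds the decision rule, lists the two principal comparisons in each trial and then states: "Treatment effects will be estimated with 95% confidence intervals for all outcomes". It continues: "Statistical significance will be at the 5% level and corresponding confidence intervals will be derived". Protocol 6.3 says that the POP-SS analysis "will estimate the mean differences (and 95% confidence interval) between the intervention and control groups".

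Neither document names a Bonferroni or other adjustment for the two comparisons at analysis. The only stricter level is 2P<0.01, for subgroup interactions (Protocol 6.4 and the SAP's Subgroup analyses).

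**The concern.** A sample size computed at 0.025 controls no error by itself. The protection comes from the rule used to judge the result, and that rule is 5% per comparison. A comparison with p between 0.025 and 0.05 on POP-SS at 12 months would be significant under General Methods but not at the level the sample size section sets. For such a result, the headline conclusion would depend on which section of the SAP the reader applies. The trial was also made larger to pay for the stricter level, and the analysis as written does not use it.

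**Working it through.** **Inputs.** SD 8, difference 2, power 90%, alpha 0.025 and 15% dropout (SAP, Sample Size and Power Calculation). SAP Table 2 counts, with A standard repair, B synthetic mesh, C biological mesh: RCT1 253/256/255; RCT1B 178 (A) and 181 (B); RCT1C 116 (A) and 114 (C). Strata are combined with stratum as a fixed effect (SAP, Primary/Secondary Outcomes).

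**1. The plan's own figure.** n per arm = 2(z₁₋α/₂ + z₀.₉₀)²/d², with d = 2/8 = 0.25.
- Two-sided 0.025: 2(2.2414 + 1.2816)²/0.0625 = 397.2, so 398. The plan's 400 is reproduced.
- Two-sided 0.05: 2(1.9600 + 1.2816)²/0.0625 = 336.2, so 337. One-sided 0.025 gives the same 337, and one-sided 0.05 gives 275.

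Only two-sided 0.025 matches. For the secondary trial, 620 × 0.85/3 = 175.7 per arm gives a detectable effect of (2.2414 + 1.2816)√(2/175.7) = 0.376, against 0.38 stated.

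**2. Correlation of the two primary-trial estimates.** Each stratum carries weight w = nₐnₓ/(nₐ + nₓ).
- A v B: 253×256/509 + 178×181/359 = 127.25 + 89.74 = 216.99.
- A v C: 253×255/508 + 116×114/230 = 127.00 + 57.50 = 184.49.
- Only the RCT1 controls are shared, so ρ = (127.25 × 127.00/253)/√(216.99 × 184.49) = 63.87/200.08 = 0.32.

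The same calculation gives 0.50 for RCT1 alone. From SAP Table 3 it gives 0.38 for the secondary trial (RCT2 plus RCT2B for A v B, RCT2 alone for A v C).

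**3. Chance of at least one false significant difference**, either direction = 1 − P(|Z₁| < c and |Z₂| < c), bivariate normal, with c = 1.960 (5%) or 2.241 (2.5%).

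| Case | ρ | 5% each | 2.5% each |
|---|---|---|---|
| Primary, combined strata | 0.32 | 9.48% | 4.83% |
| Primary, RCT1 alone | 0.50 | 9.07% | 4.64% |
| Independent tests | 0 | 9.75% | 4.94% |
| Secondary trial | 0.38 | 9.36% | 4.78% |

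Counting only false results in favour of at least one mesh arm, the primary combined-strata case gives 1 − P(Z₁ < c and Z₂ < c) = 4.7% at 5% each and 2.4% at 2.5% each.

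**4. The band in dispute, and power.** SE = SD/√(0.85 × W), W being the summed weights. The smallest significant difference is c × SE. Power for 2 points is Φ(2/SE − c). For A v B at SD 8, SE = 8/√(0.85 × 216.99) = 0.589; for A v C it is 8/√(0.85 × 184.49) = 0.639. Appendix IV of the protocol uses SD 7, so both are shown.

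| SD | Comparison | Smallest significant difference, 5% v 2.5% | Power, 5% v 2.5% |
|---|---|---|---|
| 8 | A v B | 1.15 v 1.32 | 92% v 88% |
| 8 | A v C | 1.25 v 1.43 | 88% v 81% |
| 7 | A v B | 1.01 v 1.16 | 97% v 95% |
| 7 | A v C | 1.10 v 1.25 | 95% v 91% |

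These figures assume 85% response and no gain from covariate adjustment.

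**The case against.** **The 5% may be meant as the overall level.** The same paragraph fixes 95% intervals for every outcome and ties the intervals to the 5% level. With no adjustment named, that reads as a rule per comparison. At best the text is ambiguous.

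**Two separate questions may need no adjustment.** That position is defensible in general. But the plan separates the two trials from each other, not the two comparisons within a trial, and for the primary trial it states that the pair is to share 0.05. If the sponsor prefers no adjustment, that statement has to go.

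**The effect is narrow.** This stands. Estimates and models do not change, a reader given an exact p value could apply 0.025, and the disputed differences all lie below the 2 points the trial was sized to detect.

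**The stricter level costs power.** This also stands. A v C has 369 women per arm in Table 2, or about 314 at 85% response, against the 400 wanted.

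A reader might infer more than the documents support:
- That every comparison is tested at 5%. Subgroup interactions are held to 2P<0.01.
- That there is a 9.5% chance of wrongly favouring mesh. The 9.5% counts false differences in both directions; in favour of mesh it is about 4.7%.
- That the error should be pooled over both trials, giving about 18% (1 − (1 − 0.0948)(1 − 0.0936)). The documents treat the two trials as separate families.
- That the reason for 0.025 is given for both trials. It is given only for the primary trial.

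**Conclusion.** The inconsistency is real and stands in the current text of both documents. The principal comparisons are sized at two-sided 0.025 and judged at 0.05, so the error control claimed in the sample size sections is not carried into the analysis. In the primary trial the chance of at least one false significant difference on POP-SS is about 9.5% (9.1% for RCT1 alone, 9.75% if the tests were independent) instead of about 4.8%. These figures rest on normal approximations, equal variances across arms, the randomised counts in Table 2 and one test per comparison. They do not count the second primary patient-reported outcome, the SAP's two estimates per comparison in the primary trial, or interim analyses.

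This should be fixed, but it does not undermine the trial. It changes a conclusion only when p falls between 0.025 and 0.05, which at SD 8 means observed differences of about 1.15 to 1.32 points (A v B) or 1.25 to 1.43 points (A v C).

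**What to change.** In the SAP's General Methods, state that within each trial the two principal comparisons on POP-SS at 12 months are each tested at two-sided 2.5% and reported with 97.5% confidence intervals. Name the one estimate per comparison to which this applies, for example the combined-strata model where strata are combined. Without that, having both an RCT1 estimate and a combined one leaves two chances per comparison. Make Protocol 6.3 match.

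The alternative is to keep 5% and 95% intervals and withdraw, from the SAP's sample size section and Protocol 2.7.2, the statement that the overall 0.05 is maintained.

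Holm should not be offered as interchangeable with 97.5% intervals. If one p value is below 0.025 and the other lies between 0.025 and 0.05, Holm rejects both while the second 97.5% interval still includes zero. The rules for secondary outcomes and the 2P<0.01 for subgroups can stay as they are.

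The cost is wording in both documents and intervals about 14% wider (2.2414/1.9600 = 1.14) for the principal comparisons. At the numbers recruited, power for a 2-point difference is the lower figure of each pair in the table above. At worst (A v C, SD 8) that is 81% instead of 88%, before any gain from covariate adjustment. The choice should be recorded before comparative results are seen.
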